## 1. Protocol

The broad objective of our study was to examine the potential effect of Cannabidiol (CBD) on human learning and memory (L&M) in relatively small scale surveys, and with consideration of other confounding factors (i.e., other drugs being specifically combined with CBD or particular preexisting medical conditions). Our study design aimed to determine whether CBD, when administered alone to healthy human subjects is a modulator of human L&M. We also aimed to determine whether particular demographic factors present in the general population (e.g., age, sex, history of CBD use, and urine THC) would affect the modulatory effect of CBD on L&M.

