### a. Design and Participants

57 human volunteers were recruited from the Front Range communities in Colorado (Pueblo, Colorado Springs and Denver). Subjects were randomized to two treatment arms: 1) to receive CBD First; 2) to receive placebo first. Each applicant signed an informed consent form and filled out a demographics questionnaire. The L&M for each subject was tested after administration of 246 mg CBD absolutely or placebo. Testers were blinded as to whether someone is getting CBD or Placebo. The principal investigator remained unblinded, and was not be involved in data collection nor analysis to prevent any bias. Generation of the randomization list was performed by the principal investigator.

After administration of CBD or placebo the participants waited 2hrs before taking the learning and memory tests. The experiment was repeated one week later, by reversing the CBD and control groups, in order to eliminate (or minimize) the placebo effect.

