## 2. Statistical Analysis Plan

All statistical analyses were performed using SPSS. Linear Mixed Models (LMM) with Bonferroni Corrections were used to examine L&M scores of placebo and CBD recipients, while also controlling for demographic factors. Two-tailed  $P < 0.05$  will be considered statistically significant. Subject IDs were included as random effects. Treatment (CBD vs placebo) was included as a factor. The following were included as covariates: age, history of CBD use (user or non-user), sex (male or female), and urine THC result (THC positive or negative). A Linear Mixed model was created for each of the following dependent variables: MOCA, Sum of List A trials, List B, PI Ratio, RI Ratio, FS Ratio, and Total Prose Recall.

COVID as a factor was removed from the Linear Mixed Models. Data related to COVID will be independently analyzed in a separate statistical model and reported later.

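### The first aim concerns CBD given alone, but the plan's only CBD-placebo contrast averages over THC-positive people and people with a history of CBD use, and additive covariates do not change that

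*Combined protocol and SAP*

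**What the plan says.** The opening of section 1 (Protocol) states two aims. The first is whether "CBD, when administered alone to healthy human subjects is a modulator of human L&M". The second is whether age, sex, CBD history and urine THC "would affect the modulatory effect of CBD on L&M". The same paragraph gives, as examples of confounding factors to consider, "other drugs being specifically combined with CBD or particular preexisting medical conditions".

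Section 1a (Design and Participants) describes a two-period crossover: "57 human volunteers were recruited from the Front Range communities in Colorado", "Subjects were randomized to two treatment arms: 1) to receive CBD First; 2) to receive placebo first", and "The experiment was repeated one week later, by reversing the CBD and control groups".

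Section 2 (Statistical Analysis Plan) fits one linear mixed model to each of seven outcomes. Each has a random effect for subject, one treatment factor (CBD or placebo) and four covariates: age plus "history of CBD use (user or non-user), sex (male or female), and urine THC result (THC positive or negative". The stated purpose is to compare scores "while also controlling for demographic factors". No treatment-by-covariate term is listed, and no analysis is restricted by THC status or CBD history.

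**The concern.** The two-level coding of CBD history and urine THC, together with the second aim, indicates that people with a CBD history and THC-positive people are in the analysed sample. The documents give no counts. In a THC-positive participant, the active visit may combine CBD with THC. That is close to the kind of combination that section 1 sets out as something to consider.

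A reader who sees a CBD effect from a model with THC and CBD history among its covariates may take those two influences to have been removed, leaving the effect of CBD alone. In a crossover they have not been removed. A covariate that takes one value per person moves that person's CBD and placebo scores by the same amount. The model therefore has no estimate specific to participants without other cannabinoids, and the first aim could be answered with a number that describes a different population.

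**Working it through.** The plan states no effect size, SD or power figure, so there is nothing of its own to reproduce. The check is algebra, confirmed by simulation.

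**Inputs from the documents.** 57 participants, two visits each (section 1a). Random subject effect, one treatment factor, four additive covariates (section 2).

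**Assumed inputs.** The share q who are THC-positive or have a CBD history, the effect in each group, and the SDs (between-person 1.5, within-person 1.2 in the simulation).

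**Step 1: the covariates cancel.** The planned model for person i at visit j is y_ij = μ + τ·T_ij + β′x_i + b_i + e_ij. The within-person difference is

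D_i = y_i(CBD) − y_i(placebo) = τ + e_i(CBD) − e_i(placebo).

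β′x_i drops out, and with complete pairs the estimate of τ is the mean of D_i with or without covariates. In simulated 57-person crossovers with complete data, adding all four covariates moved the treatment estimate by at most about 10⁻¹⁴ (rounding error) and its SE by under 0.000004.

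**Step 2: limits of that result.**
- Missing visits: with 3, 6 or 12 of 57 people lacking one visit, the largest change was 0.028, 0.033 and 0.056, against an SE of about 0.24 to 0.25. The change is small but not zero.
- Urine THC measured at each visit: x_i becomes x_ij, and D_i gains the term β·(x_i(CBD) − x_i(placebo)). The estimate can then move. Section 2 does not say how often urine was tested.

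**Step 3: what the pooled contrast estimates.** Let the effect be τ₀ in THC-negative participants without CBD history and τ₁ on average in the rest. Then

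pooled effect = (1 − q)·τ₀ + q·τ₁, and gap = τ₀ − pooled = q·(τ₀ − τ₁).

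The gap is zero if τ₀ = τ₁. For illustration, set τ₀ = 1.0 (means over 40 simulated trials per row):

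| Restricted n of 57 | τ₁ | Pooled, by formula | Pooled, additive model | Restricted model |
|---|---|---|---|---|
| 51 | 0 | 51/57 = 0.89 | 0.88 | 0.98 |
| 40 | 0 | 40/57 = 0.70 | 0.69 | 0.98 |
| 40 | 0.5 | (40 + 8.5)/57 = 0.85 | 0.84 | 0.98 |
| 28 | 0 | 28/57 = 0.49 | 0.48 | 0.98 |
| 28 | 0.5 | (28 + 14.5)/57 = 0.75 | 0.73 | 0.98 |

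**Step 4: precision of a restricted estimate.** With equal within-person variance in the groups, the SE ratio (restricted to pooled) is 1/√(1 − q): 1.12, 1.29 and 1.58 for q = 0.2, 0.4 and 0.6. In the simulation with τ₁ = 0, the SE rose from 0.23 to 0.27 (n = 40) or 0.32 (n = 28). The standardised paired effect detectable with 80% power at two-sided 0.05, before any Bonferroni correction, is (1.960 + 0.842)/√n: 0.37 for n = 57, 0.44 for n = 40 and 0.53 for n = 28.

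**The case against.** The strongest reply is that the first aim is met as written. Giving CBD alone can mean that no other study drug accompanies it, and section 1a gives only CBD or placebo. Section 1 deliberately takes in CBD history and urine THC as features of the general population, so a mixed sample is intended. The pooled contrast is a fair within-person average for that sample. It departs from the restricted contrast only if the effect varies with THC status or CBD history, which is the second aim's question. All of this stands. It makes the matter one of labelling and a missing supportive estimate, not of an invalid analysis.

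Four stronger readings are tempting, and the documents do not support them:
- *The pooled contrast is confounded by THC or CBD history.* Each person is their own control, so an additive influence present at both visits cancels.
- *The sample contains current CBD users, whose placebo visit is not free of CBD.* Section 2 records a history of use without saying how recent. The sections available state no restriction on own use, but the text is short and part of it was removed, so silence shows little.
- *The effect is diluted by a known amount.* Every figure in the table rests on assumed shares and effects.
- *The plan claims that its covariates isolate CBD alone.* Section 2 says only that demographic factors are controlled for.

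The reply does not supply an estimate for participants without other cannabinoids. Nor does it give additive covariates a role in producing one.

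**Conclusion.** The point holds in a limited form. No planned estimate isolates CBD in THC-negative participants without CBD history, although section 1 asks about CBD given alone and names other drugs combined with it as a factor to consider. The additive covariates leave the pooled contrast exactly unchanged if every participant has both visits and one value per covariate. They leave it nearly unchanged if a few visits are missing. Invariance is not guaranteed if urine THC was measured at each visit.

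The gap is q·(τ₀ − τ₁). Neither q nor the effects are in the documents, so it could be nil or material. It matters only if the CBD effect varies with THC status or CBD history, a possibility that the second aim itself raises. This is an inexpensive improvement and does not invalidate the main analysis.

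**What to change.** In section 2:

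1. Either add treatment-by-urine-THC and treatment-by-CBD-history terms to each model, which the second aim needs in any case, or rerun the same model in THC-negative participants without CBD history. The two routes need not give identical estimates: two separate interaction terms assume that the two modifications add up in people who have both features. Name one route as the reported one.
2. Report the CBD-placebo contrast with its interval for THC-negative participants without CBD history, as a prespecified supportive estimate beside the all-participant contrast. If results have already been seen, say that it was added afterwards. Give the number in the restricted group.
3. Label the all-participant contrast as the average effect in a sample that includes THC-positive people and people with a history of CBD use. Do not describe the covariates as removing the influence of THC or CBD history on the treatment effect.
4. State how CBD history was defined and whether urine THC was taken once or at each visit.

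The cost is wording and, at most, one further run of each model on data that section 2 already uses. The supportive interval will be wider, by a factor of about 1/√(1 − q) with q unknown. There will also be one extra contrast for each of seven outcomes, which should be read as supportive and not as a further confirmatory test.

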### a. Design and Participants

57 human volunteers were recruited from the Front Range communities in Colorado (Pueblo, Colorado Springs and Denver). Subjects were randomized to two treatment arms: 1) to receive CBD First; 2) to receive placebo first. Each applicant signed an informed consent form and filled out a demographics questionnaire. The L&M for each subject was tested after administration of 246 mg CBD absolutely or placebo. Testers were blinded as to whether someone is getting CBD or Placebo. The principal investigator remained unblinded, and was not be involved in data collection nor analysis to prevent any bias. Generation of the randomization list was performed by the principal investigator.

After administration of CBD or placebo the participants waited 2hrs before taking the learning and memory tests. The experiment was repeated one week later, by reversing the CBD and control groups, in order to eliminate (or minimize) the placebo effect.

## b. Cognitive Assessments

Each subject will be required to take two 30-min tests (Version 1 L&M test and Version 2 L&M test). Each test compromised of two sessions: session A, session B, and session C. Test session A was an assessment of basal cognitive function, session B was a verbal declarative memory test, and session C was a prose recall-cognitive L&M test (Schoeler and Bhattacharyya 2013).

First, participants were asked to complete the Montreal Cognitive Assessment (MOCA) as part of session A. The MOCA was given by a tester and took 5-10 minutes. This was a written non-invasive assessment of basal cognitive function. The purpose of the prose test was to evaluate logical memory in study subjects (Curran et al. 2002, Morgan et al. 2010, Hindocha et al. 2018).

For the verbal declarative memory test (session B), we used the Rey-Auditory Verbal Learning Test-Revised (RAVLT-R) test (Solowij et al. 2011, Meier et al. 2012, Schoeler and Bhattacharyya 2013, Becker et al. 2014, Khosravi Fard et al. 2016). Participants were instructed to listen to a list of 12 words (List A) read to them. They were asked to recall List A in four trials, with the words repeated to them during each trial. The number of words the participants remember was expected to increase between trials 1 and 4. The purpose of the multiple trials was to check if list learning is enhanced. Participants were scored for the number of correctly repeated words for each trial and for the number of intrusions (number of words not on list). Participants were also be scored for clusters (number of words said consecutively that were in the same semantic category). Then, the participants were instructed to listen to another list of 12 words (List B), asked to recall List B once, and scored

for the number of correctly repeated words. Afterward, participants were asked to recall List A and were scored for the number of correctly repeated words.

Participants were instructed to listen to a short prose story (Passage I) and asked to immediately recall the passage as part of session C. Then, the participants were asked a series of questions about Passage I and given a score of 0 if they said the incorrect answer and a score of 1 if they got the right answer. Scores were added. Participants were distracted with delayed recall of list A. Afterward, participants were asked to recall passage I.

The test sessions were conducted at CSU-Pueblo in Pueblo.

c. L&M data collection from participants

The learning and memory scores collected from participants included MOCA performance, RAVLT-R performance (List A trials: A1, A2, A3, A4, A5, A6, A7, sum of list A trials; List B trial: B), and prose recall performance (immediate, delayed, and total). The effects of two types of interference from the RAVLT-R were quantified as:

- 1) Proactive Interference:  $(PI) = \frac{B}{A1}$ , where B is the number of words recalled from List B (distractor list), and A1 is the number of words recalled from list A on the 1st trial
- 2) Retroactive Interference  $(RI) = \frac{A6}{A5}$ , where A6 is the number of words recalled from List A after the distractor List B, and A5 is the number of words recalled from List A on the 5th trial.

Assessing Proactive Interference allowed for the determination of how learning old material impacts learning new information. In this study, effects of proactive interference were determined

by seeing how List B recall was impacted after List A recall. Assessing Retroactive Interference allowed for determination of how newly acquired information impacts the recall of previously learned information. In this study, effects of retroactive interference were determined by seeing how immediate recall is impacted after List B recall by comparing trial 5 recall (before List B) and immediate recall (after List B). These equations were utilized by Magalhães (et al., [2012](#)) to evaluate the PI, RI, and FS Ratios and the ratios have been used in other L&M studies (Geffen et al., [1990](#); Vanderploeg et al., [2001](#); Kramer et al., [1991](#); Numan et al., [2000](#); Torres et al., [2001](#); Malloy-Diniz et al., [2007](#); Magalhães et al., [2012](#); Frith et al., [2018](#)).

## 2. Statistical Analysis Plan

All statistical analyses were performed using SPSS. Linear Mixed Models (LMM) with Bonferroni Corrections were used to examine L&M scores of placebo and CBD recipients, while also controlling for demographic factors. Two-tailed  $P < 0.05$  will be considered statistically significant. Subject IDs were included as random effects. Treatment (CBD vs placebo) was included as a factor. The following were included as covariates: age, history of CBD use (user or non-user), sex (male or female), and urine THC result (THC positive or negative). A Linear Mixed model was created for each of the following dependent variables: MOCA, Sum of List A trials, List B, PI Ratio, RI Ratio, FS Ratio, and Total Prose Recall.

COVID as a factor was removed from the Linear Mixed Models. Data related to COVID will be independently analyzed in a separate statistical model and reported later.

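### If the Bonferroni correction is meant to cover the seven treatment tests, Holm's step-down would give the same error control and never fewer rejections; the SAP should name it and state the family

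*Combined protocol and SAP*

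**What the plan says.** All of the text on this point is in section 2 (Statistical Analysis Plan).

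- **Method:** "Linear Mixed Models (LMM) with Bonferroni Corrections were used to examine L&M scores of placebo and CBD recipients". No other multiplicity procedure is mentioned.
- **Outcomes:** "A Linear Mixed model was created for each of the following dependent variables", and the list is "MOCA, Sum of List A trials, List B, PI Ratio, RI Ratio, FS Ratio, and Total Prose Recall". That makes seven models. None is marked as primary and there is no testing order.
- **Treatment term:** "Treatment (CBD vs placebo) was included as a factor". It has two levels, so there is one treatment comparison per model. Four covariates are also in each model; the SAP does not say whether their tests count towards the correction.
- **Threshold:** two-tailed P below 0.05 "will be considered statistically significant". No divided threshold is given, and nothing says whether the P values are already adjusted.

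The protocol (section 1a, Design and Participants) gives the size and design: "57 human volunteers were recruited from the Front Range communities in Colorado", and "The experiment was repeated one week later, by reversing the CBD and control groups". There is no sample-size or power calculation.

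**The concern.** With no primary outcome, the trial's answer is a list of the outcomes on which CBD and placebo differ. The multiplicity method decides how long that list can be. Single-step Bonferroni over seven tests keeps the strictest threshold for every outcome, however many others have already been rejected. Holm's procedure relaxes the threshold after each rejection, needs no added assumption, and gives the same family-wise guarantee.

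If CBD affects several outcomes, some could be left off the list that an equally rigorous method would have put on it. Nothing in the documents shows that a study of 57 people has power to spare.

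**Working it through.** **Inputs from the documents.** Alpha 0.05 two-tailed; seven outcome models; one treatment comparison per model; 57 people, each tested under both conditions. The documents state no power or adjusted alpha, so there is no figure of theirs to reproduce.

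**Assumptions not in the documents.** All 57 give complete pairs. Each affected outcome has a standardised within-person effect dz (mean difference divided by the SD of the differences). The seven differences share a common correlation. The number of truly affected outcomes is varied.

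**Step 1: thresholds, if the family is the seven treatment tests.**

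- Bonferroni: 0.05/7 = 0.0071 for every test.
- Holm, from smallest to largest p: 0.05/7, 0.05/6, …, 0.05/1 = 0.0071, 0.0083, 0.0100, 0.0125, 0.0167, 0.025, 0.05, stopping at the first failure.

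The first Holm threshold equals Bonferroni's and the later ones are larger. So Holm rejects everything Bonferroni rejects, and the two make at least one rejection in exactly the same data sets.

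**Step 2: error control.** Suppose m0 of the seven nulls are true. When Holm first rejects a true null, all m0 true nulls are still in the running, so the threshold at that step is at most 0.05/m0. By the union bound, the chance of this is at most m0 × 0.05/m0 = 0.05. Nothing is assumed about correlation. Under the global null with independent tests, both methods give 1 − (1 − 0.05/7)^7 = 4.9%.

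**Step 3: power.** A hand check at dz 0.4 with normal tests: 0.4 × √57 = 3.020; the two-sided critical value at 0.00714 is 2.690; Φ(3.020 − 2.690) = 63%. Simulation of the same case gave 63.0% for Bonferroni.

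Simulated paired t-tests (56 df), correlation 0 to 0.6, average power per affected outcome:

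| Affected outcomes | dz | Bonferroni | Holm | Gain (points) |
|---|---|---|---|---|
| 1 of 7 | 0.45 | 73% | 73% | about 0.1 or less |
| 2 of 7 | 0.45 | 72–73% | 73–74% | about 1 |
| 4 of 7 | 0.45 | 72–73% | 76–77% | 4–5 |
| 7 of 7 | 0.35 | 45% | 55% | 10 |
| 7 of 7 | 0.45 | 72–73% | 83–87% | 10–14 |

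With three affected, the gain was 2 to 3 points at dz 0.35 to 0.45. Normal-test runs over dz 0.3 to 0.5 and correlation 0 to 0.5 gave 1.4 to 2.7 points with three affected and 5.9 to 13.2 with seven. The chance of finding all seven at dz 0.45 was 10–38% with Bonferroni and 50–69% with Holm. Holm's family-wise error stayed below 5% in every scenario.

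**Step 4: role of correlation.** With all seven affected at dz 0.45, the gain fell from about 14 points at correlation 0 to about 10 at 0.6. At dz 0.3 it rose from 5.9 points (39.4 − 33.5) at correlation 0 to 7.7 (41.25 − 33.58) at 0.5. Correlation has no consistent direction; the number of affected outcomes drives the gain.

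**Step 5: the other reading.** If the correction is applied inside each model to the two-level treatment factor, there is one comparison, the threshold is 0.05/1 = 0.05, and Holm saves no power. The seven treatment tests are then uncorrected as a set: family-wise error is 1 − 0.95^7 = 30.2% if independent, 22.9% at correlation 0.5, and at most 7 × 0.05 = 35%.

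**The case against.** The strongest reply is that plain Bonferroni is a valid method, no figure in the plan is wrong, and no stated power target is missed. A preference for Holm could be raised against any plan that uses Bonferroni. That stands: this is a point about efficiency.

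The SAP also never says that the correction spans the seven outcomes. A within-model correction would do nothing to a two-level factor, which favours the across-outcome reading, but the undivided 0.05 leaves both open. Under the within-model reading the trouble is too many false positives, not lost power. That stands too, and it is why the point is conditional and why the fix names the family.

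A reader might infer that the shared word-list scores make the outcomes move together and that this is where Holm gains most. The documents do not support that. Section 1c of the protocol defines proactive interference as B/A1 and retroactive interference as A6/A5. A proportional shift in numerator and denominator leaves a ratio unchanged, and a rise in A1 alone raises the List A sum while lowering B/A1. Nor did correlation consistently raise the gain (step 4).

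Finally, the SAP is written largely in the past tense. If the results are already known, moving to a more permissive procedure is a post hoc choice and not only a change of wording.

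**Conclusion.** The point holds conditionally. If the family is the seven treatment tests, Holm keeps the 5% family-wise error under any dependence and never rejects fewer outcomes. With 57 complete pairs, the gain per affected outcome is negligible when one outcome is affected, about 1 point with two, up to 3 with three, 4 to 5 with four at dz 0.45, and 10 to 14 with all seven at dz 0.35 to 0.45. These sizes rest on assumed effects and on a number of affected outcomes that the documents do not give. The large gains need CBD to act on most or all of the seven.

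A reader might go further and infer that real effects will be missed for nothing. The documents do not support that: they give no effect sizes, they do not confirm that the correction spans the outcomes, and the chance of at least one finding is the same under either method. Nor is Holm entirely without cost, because simultaneous intervals become less direct. Bonferroni is not an error here. I would label this a cheap improvement.

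**What to change.** In section 2 of the SAP, replace the reference to Bonferroni with: *Holm step-down adjustment of the seven treatment (CBD vs placebo) p-values, one per outcome model; Holm-adjusted two-tailed P < 0.05 is significant.* This also states the family, the number of tests and what the 0.05 refers to, so it resolves both readings of the current text. Covariate tests then lie outside the family.

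To apply it, order the p-values from p(1) to p(7), multiply p(i) by (8 − i), carry the running maximum forward, and cap at 1.

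The cost is one sentence and a spreadsheet step on seven numbers, with no loss of family-wise error control. Simultaneous confidence intervals are less direct under Holm than under Bonferroni, so report ordinary 95% intervals beside the adjusted p-values and say that they are unadjusted. If the results have already been seen, label the change post hoc and show the Bonferroni result beside the Holm result.

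### The crossover mixed models have no period or test-version term, so a week-to-week shift inflates the standard error of the CBD effect and, with unequal sequences or losses, biases it

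*Combined protocol and SAP*

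**What the plan says.** Section 1.a (Design and Participants) describes a two-period crossover: "Subjects were randomized to two treatment arms: 1) to receive CBD First; 2) to receive placebo first", and then "The experiment was repeated one week later, by reversing the CBD and control groups". It reports that "57 human volunteers were recruited from the Front Range communities in Colorado" but gives no allocation ratio, blocking or number per sequence. Section 1.b (Cognitive Assessments) has each subject take "two 30-min tests (Version 1 L&M test and Version 2 L&M test". It does not say whether version followed week, followed treatment or was counterbalanced.

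Section 2 (Statistical Analysis Plan) sets out the model: "Subject IDs were included as random effects. Treatment (CBD vs placebo) was included as a factor". It continues: "The following were included as covariates: age, history of CBD use (user or non-user), sex (male or female), and urine THC result". The same structure serves seven outcomes ("A Linear Mixed model was created for each of the following dependent variables"): MOCA, Sum of List A trials, List B, the PI, RI and FS ratios, and Total Prose Recall. Section 2 also says that COVID was taken out of the models, so the list reads as a deliberate account of their terms. No period, week, sequence or version term appears in either document section, and nothing is said about missed second visits.

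**The concern.** Memory tests of the same kind are given twice, a week apart. A gain at the second visit is plausible, and the two versions may differ in difficulty. In a crossover such a shift raises the CBD-minus-placebo difference in one sequence and lowers it in the other. A model with treatment and subject alone has nowhere to put this spread except the residual. Reversing the treatments balances the average only when sequences and losses are equal, and it never restores the standard error. Because 57 is odd, exact balance is impossible even with no losses.

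What is at stake is the central CBD-placebo contrast. Near balance, a real effect is more likely to be missed and the confidence interval is too wide. With a clearly uneven split, the shift moves the estimate in the direction of the imbalance and can hide an effect or create one.

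**Working it through.** The documents contain no sample-size, power or standard-error figure, so there is nothing to reproduce first.

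**Inputs.** N = 57 (section 1.a); two-sided α = 0.05 (section 2). All else is assumed: true effect τ = 0.3 outcome SD; week-2 shift π = +0.1 to +0.5 SD; within-subject correlation r = 0.7 or 0.5; complete pairs unless stated; the four covariates constant within subject (when urine THC was tested is not stated). Splits are written CBD-first/placebo-first, with counts n_C and n_P.

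**Step 1: the estimate.** Let d = CBD minus placebo. Its mean is τ − π in CBD-first subjects and τ + π in placebo-first subjects. With complete pairs the planned model reduces to the paired difference, so its expected value is τ + π(n_P − n_C)/N. At π = 0.5 the bias is:
- 29/28: 0.5 × (−1)/57 = −0.009 SD
- 33/24: 0.5 × (−9)/57 = −0.079 SD
- 35/22: 0.5 × (−13)/57 = −0.114 SD

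**Step 2: the standard error.** With a period term, Var(d) = 2(1 − r). Without it, π² × 4·n_C·n_P/N² is added. At 29/28 the multiplier is 3248/3249, so the addition is essentially π². The SE ratio is √[(2(1 − r) + π²) / (2(1 − r))]; for r = 0.7 and π = 0.5 that is √(0.85/0.6) = 1.190. Simulated power (200,000 replicates per cell) is shown from 29/28 (low end) to 28/29 (high end):

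| π (SD) | SE ratio, r=0.7 | Power without period, r=0.7 | SE ratio, r=0.5 | Power without period, r=0.5 |
|---|---|---|---|---|
| 0.1 | 1.008 | not run | 1.005 | not run |
| 0.2 | 1.033 | 79.2-81.3% | 1.020 | 57.8-60.1% |
| 0.3 | 1.072 | 76.3-79.3% | 1.044 | 55.5-58.5% |
| 0.5 | 1.190 | 67.3-73.0% | 1.118 | 48.6-53.7% |

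With a period term, power is 81.9-82.1% (r = 0.7) and 60.3-60.6% (r = 0.5). Reversing the sign of π or of the effect swaps the two directions.

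REML random-intercept fits with four covariates (π = 0.5, r = 0.7) gave a mean model SE of 0.121-0.123 without period and 0.102-0.103 with it. This matches √(0.85/57) = 0.122 and √(0.6/57) = 0.103. The actual spread of the estimates was 0.097-0.104 and the same in both models. Near balance, then, the estimate itself is no noisier; its reported SE is wrong.

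**Step 3: type I error by split, period omitted.**

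| Split | π=0.5, r=0.7 | π=0.5, r=0.5 | π=0.2, r=0.7 |
|---|---|---|---|
| 29/28 | 2.0% | 2.9% | 4.4% |
| 32/25 | 4.3% | 4.5% | 4.9% |
| 33/24 | 5.9% | 5.8% | 5.3% |
| 35/22 | 11.1% | 9.3% | 6.3% |

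At π = 0.5 the period-adjusted model holds 5.0-5.1% throughout. With the 0.3 SD effect present (π = 0.5, r = 0.7), rejection without period is 48.3% at 32/25 and 86.7% at 25/32, against 81.5% and 81.1% with period. If randomisation was simple, Binomial(57, 0.5) gives probability 0.289 for a split at least as uneven as 33:24 and 0.111 for 35:22.

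**Step 4: missed second visits** (29/28 start, π = 0.5). Three lost in each sequence gives a bias of −0.010 SD. Six lost from placebo-first only gives −0.054 to −0.060 SD; six lost from CBD-first only gives +0.035 to +0.040 SD. In the loss patterns checked with a period term, the bias is zero.

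**Step 5: ratio outcomes.** A common gain partly cancels in PI and RI. With A1 and B both assumed at mean 6 words, SD 1.6 and correlation 0.4, a 0.5 SD gain in both moves PI by only about 0.04 SD. FS has no formula in the documents.

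**The case against.** The omission is certain but the harm is not. The documents give no value for the shift, correlation, split or dropout, and the striking figures come from the top of the assumed range. At π = 0.2 and r = 0.7, near-balanced power falls by only about 1 to 3 points, and type I error stays between 4.4% and 6.3% across the splits shown. Two test versions may reduce recall of memorised items and so make a large shift less likely. Near balance the test is conservative, so a positive finding would survive. The false-positive case needs an uneven split, which a blocked list would make unlikely. Averaged over simple 1:1 randomisation, the test without period is unbiased and holds 5%.

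All of this is fair and limits the size of the point. It does not remove it. Alternate versions rule out neither a general practice gain nor a difference in difficulty. The unconditional 5% does not help once a particular uneven split has occurred. A conservative test also matters for a study of 57 people, in which a null result is hard to interpret.

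Version tied to treatment is a separate possibility that no text suggests, and it would sit awkwardly with blinded testers. If it had happened, a 0.2 SD version difference would bias the CBD effect by 0.20 SD at any split, and a period term would not help. It is a reason to report version assignment and adds no weight here.

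**Conclusion.** The concern holds and should be fixed. The stated model contains no term for week or version, and both consequences follow by algebra. With near-equal sequences the problem is an over-wide interval and a conservative test. SE inflation runs from under 1% at a 0.1 SD shift to 19% (r = 0.7) or 12% (r = 0.5) at 0.5 SD. Bias becomes material only with clearly uneven sequences or one-sided losses, reaching 0.11 SD at 35:22 with a 0.5 SD shift. The analysis is inefficient rather than invalid. The presence of the defect is certain; its size is conditional on assumed inputs. The argument applies most strongly to MOCA, Sum of List A trials, List B and Total Prose Recall, and these sizes are not claimed for the ratios.

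**What to change.** Add period (week 1 or week 2) as a fixed effect in each of the seven models, and report the period-adjusted CBD-placebo contrast with its confidence interval. Handle version according to how it was assigned:

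- **Counterbalanced:** add version as a fixed effect.
- **Tied to week:** the period term absorbs it and the two cannot be separated.
- **Tied to treatment:** state as a limitation that the version difference biases the CBD effect and that no model term can remove it.

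Report the number randomised, completers and missed visits per sequence, and how versions were assigned. Section 2 is written largely in the past tense. If results have already been seen, label the period-adjusted models post hoc and show them beside the planned ones. A period term does not address carryover, which is a separate matter.

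The cost is one degree of freedom, or two with version, and a re-run of seven models. If there is no period effect, power changes by 0.1 point or less at 29/28 and 28/29 (for example 60.3% against 60.2% at r = 0.5, 28/29). Visit order follows from the assigned sequence; the version used at each visit is the only other item needed.
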